14.0 STATISTICAL CONSIDERATIONS

14.1 Phase 1

14.1.1 General Considerations: DLTs are defined in Section 8.3. DLTs occurring during Cycle 1 will be used to guide dose escalation. However, before the phase 2 portion is begun, all grade ≥ 3 adverse events of all patients treated in the phase 1 portion will be reviewed to assess for late and cumulative toxicities that were not captured during the phase 1 portion of the trial. The Principal Investigator reserves the right to modify the protocol to reduce the drug doses identified in the phase 1 portion if this assessment suggests a significant risk of late/cumulative toxicities. Patients will be considered evaluable for DLT if they received at least 75% of the assigned doses of each chemotherapeutic during Cycle 1 or if they developed a DLT. If a patient does not develop a DLT but does not receive at least 75% of treatment during Cycle 1, the patient will be considered not evaluable for DLT and will be replaced. Maximum tolerated dose (MTD) is defined as the highest dose studied in which the incidence of DLT is $<33\%$ assuming at least 6 patients have been treated at this dose.

14.1.2 Dose Escalation scheme:

Starting with dose level K=1:

A. Evaluate 6 patients at dose level K

- a. If 0 or 1 have DLT, increase dose to K+1 and go to A
- b. If 2 have DLT, stop dose escalation
- c. If >2 have a DLT, go to dose K-1

The dose level below that which dose escalation was stopped is the potential MTD.

In order to better define safety and initial evidence of anti-leukemia activity while waiting for patients to complete their treatment cycles to assess the MTD, any dose level cohort may be expanded up to 12 patients, provided that

2 or fewer of 6 patients had DLT at that dose level (ie at least 4/6 have had no DLT). the cohort is expanded to 7-11 patients, these patients will not count toward DLT and MTD evaluation. If a cohort is expanded to 12 patients, the following rules will determine further dose escalation:

If 3 or fewer have DLT, increase dose to K+1 (go to A)

If 4 or more have DLT, stop dose escalation

Dose-finding for both mitoxantrone and sorafenib:

Level 1	Mitoxantrone10 mg/m ²	Sorafenib 200 mg BID
Level 2	Mitoxantrone12 mg/m ²	Sorafenib 200 mg BID
Level 3	Mitoxantrone15 mg/m ²	Sorafenib 200 mg BID
Level 4	Mitoxantrone18 mg/m ²	Sorafenib 200 mg BID
Level 5	Mitoxantrone18 mg/m ²	Sorafenib 400mg AM, 200 mg PM
Level 6	Mitoxantrone18 mg/m ²	Sorafenib 400 mg BID

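### Two phase 1 DLT rules need correcting (the 8.3.2 exemption is reversed; 14.1.2 drops patients 7 to 11 from the MTD count), and the action at 2/6 DLTs should be fixed in advance

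*Combined protocol and SAP*

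**What the plan says.** **DLT definition (8.3.2).** Grade 4 or worse non-hematologic toxicity is a DLT, with two exemptions. Febrile neutropenia and infection are exempt unless judged a direct consequence of treatment toxicity. Constitutional symptoms are exempt on the stated condition that they have not recovered to Grade 2 or less within 14 days.

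**MTD definition (14.1.1).** "Maximum tolerated dose (MTD) is defined as the highest dose studied in which the incidence of DLT is" below 33%, with at least 6 patients treated at that dose.

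**Escalation (14.1.2).** With six patients, 0 or 1 DLT escalates. For two, "If 2 have DLT, stop dose escalation". More than two sends the trial to the level below. After a stop, "The dose level below that which dose escalation was stopped is the potential MTD".

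**Expansion (14.1.2).** To learn more about safety and activity while waiting, "any dose level cohort may be expanded up to 12 patients, provided that" "2 or fewer of 6 patients had DLT at that dose level". At 12 patients, 3 or fewer DLTs escalate and 4 or more stop. For intermediate sizes, "the cohort is expanded to 7-11 patients, these patients will not count toward DLT and MTD evaluation". I read that sentence as conditional; an opening word seems to be missing.

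**Safeguards.** Before phase 2, all Grade 3 or worse adverse events of all phase 1 patients "will be reviewed to assess for late and cumulative toxicities that were not captured during the phase 1 portion of the trial", and the principal investigator may then reduce doses (14.1.1). Section 12.0 provides for committee review of adverse events and stopping rules.

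**The concern.** The MTD is the phase 1 primary objective (2.1.1). It sets the phase 2 dose and decides which phase 1 patients enter the phase 2 analysis (14.2). Three pieces of wording bear on it.

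- **A. 8.3.2.** As worded, a persistent Grade 4 constitutional symptom is not a DLT and one that resolves promptly is. This definition feeds every escalation decision.
- **B. Patients 7 to 11.** DLTs seen in these patients are discarded when a cohort ends short of 12. A level can then be named although its observed incidence, over everyone treated there, does not meet 14.1.1.
- **C. 2/6.** The same result may stop escalation or may lead to 12 patients and possible escalation. Expansion is optional and no criterion governs it, so the choice is made with the DLTs known.

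**Working it through.** The protocol gives no phase 1 operating characteristics to reproduce and no true DLT rate. I assume rates p of 0.20, 1/3 and 0.40 and use exact binomial probabilities.

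**Cut-offs against the 33% limit.** 1/6 = 16.7% and 3/12 = 25.0% pass; 2/6 = 33.3% and 4/12 = 33.3% fail. The 6- and 12-patient rules agree with 14.1.1.

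**A. 8.3.2 by cases.**

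| Grade 4 constitutional symptom | As worded | Sensible rule |
|---|---|---|
| Recovers to Grade 2 or less within 14 days | DLT | exempt |
| Does not recover | exempt | DLT |

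Section 8.3.1 catches some persistent events, because it covers Grade 3 or worse toxicity lasting over 48 hours that delays the next cycle by more than 7 days. It does not say what happens when no next cycle is given. No magnitude can be calculated.

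**B. Cohort ending at 11.** The mismatch is 0 or 1 DLT in the first six but at least 4 in all 11 (4/11 = 36%):

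P(0/6) × P(at least 4/5) + P(1/6) × P(at least 3/5)

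- p = 0.20: 0.2621 × 0.0067 + 0.3932 × 0.0579 = 0.0245
- p = 1/3: 0.0878 × 0.0453 + 0.2634 × 0.2099 = 0.0593
- p = 0.40: 0.0467 × 0.0870 + 0.1866 × 0.3174 = 0.0633

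At level 6 these figures apply directly. Phase 1 ends when that level is completed (14.2), so no higher level has to fail first.

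At lower levels the next level must also fail. Its probability depends on how 14.1.2 is read: any result of at least 2/6 leads to naming the level below, or only exactly 2/6 does, since more than 2/6 sends the trial down a level, where more patients may be treated. Both columns assume the same rate at the next level and no expansion there.

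| p | Joint | P(at least 2/6) | Product | P(exactly 2/6) | Product |
|---|---|---|---|---|---|
| 0.20 | 0.0245 | 0.345 | 0.8% | 0.246 | 0.6% |
| 1/3 | 0.0593 | 0.649 | 3.8% | 0.329 | 2.0% |
| 0.40 | 0.0633 | 0.767 | 4.9% | 0.311 | 2.0% |

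At p = 1/3, the joint probability for cohorts ending at 7, 8, 9 and 10 is 0, 0.0293, 0.0715 and 0.0303. It is zero at 7 because 2/7 = 29% is the most that can be reached. All figures are conditional on a partial expansion.

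**C. Escalation after six patients.** If 2/6 stops: P(0 or 1 of 6). If 2/6 expands: P(0 or 1 of 6) + P(2/6) × P(0 or 1 of the next 6).

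- p = 0.20: 0.655, against 0.655 + 0.246 × 0.655 = 0.816
- p = 1/3: 0.351, against 0.351 + 0.329 × 0.351 = 0.467
- p = 0.40: 0.233, against 0.233 + 0.311 × 0.233 = 0.306

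A 2/6 result itself occurs in 25%, 33% and 31% of cohorts.

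**The case against.** **On 2/6.** A reader might infer that 14.1.2 contradicts itself, or that one branch can yield an MTD above the protocol's limit. The documents support neither. Stopping by default, with an express option to expand, is coherent and fits the 6+6 rule named in 6.0, and both branches respect 33%. The gap between 66% and 82% compares two acceptable policies and does not measure harm. Escalation decisions in an open-label phase 1 trial are always made with DLTs known. This stands; what remains is a missing criterion.

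**On patients 7 to 11.** The rule is determinate, applies only to cohorts that end short of 12, and yields only a potential MTD. The pre-phase 2 review covers all phase 1 patients, so it would be wrong to infer that their DLTs go unseen. That also stands, but the review is directed at late and cumulative toxicity, sets no DLT threshold, and leaves any dose reduction to discretion. Nor does 4/11 show that a dose is too toxic: its exact 95% interval is 11% to 69%. The point is that it fails the protocol's own definition.

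**On 8.3.2.** The intended meaning is easy to guess. A definition that decides escalation should still not depend on guessing.

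**Conclusion.** The concern holds, as a set of wording corrections that should be made.

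- **A** is a plain reversal. Its effect cannot be quantified, and 8.3.1 partly offsets it.
- **B** is a real conflict between 14.1.2 and 14.1.1, but an uncommon one. For a cohort ending at 11 it is 2.5% to 6.3% at level 6. At lower levels it is 0.8% to 4.9% or 0.6% to 2.0%, depending on how the next level's result is acted on. These figures rest on the assumed rates and must be multiplied by an unknown chance of partial expansion. They should not be read as the frequency of a wrong MTD in this trial.
- **C** is a secondary clarification.

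Two minor wording points remain. Section 8.3.1 does not say how a prolonged Grade 3 event is scored when no next cycle follows. The toxicity threshold for a second course is Grade 2 or less in 6.0 but below Grade 2 in 6.6.4 and 6.10.1; this does not bear on the MTD.

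**What to change.** 1. **8.3.2:** exempt Grade 4 or worse constitutional symptoms only if they recover to Grade 2 or less within 14 days.
2. **14.1.2:** delete the exclusion of patients 7 to 11. Before a level is declared the MTD, require a DLT incidence below 33% among all DLT-evaluable patients treated there. Check this once, after phase 1 enrolment at that level has closed and Cycle 1 assessment is complete, so that no DLT-free patient can be added to change the result. If the level fails, apply the check to the next lower one. Report the incidence with an exact 95% confidence interval.
3. Do not escalate above a level whose all-patient incidence is already 33% or more. Without this, item 2 corrects the label but not the exposure of the next cohort.
4. State one action for 2/6: stop, or expand to 12 and decide at 12. The choice is the sponsor's.
5. Settle the 8.3.1 scoring and align 6.0 with 6.6.4 and 6.10.1.

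**Cost of items 2 and 3.** The MTD may occasionally be one level too low. With assumed rates of 0.20 at the level and 1/3 at the next, the joint probabilities for cohorts ending at 8, 9, 10 and 11 are 0.0157, 0.0430, 0.0111 and 0.0245. Multiplied by 0.649 (next level at least 2/6, no expansion), an acceptable level is passed over in 1.0%, 2.8%, 0.7% and 1.6% of cases. Item 3 can raise this to at most the joint probabilities themselves, because it acts whatever the next level would have shown.

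**Cost of item 4.** Stopping gives up about 16 points of escalation chance at a true rate of 0.20. Expanding costs up to 6 more patients and adds about 12 points at 1/3.

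The documents do not say whether phase 1 has closed. If it has, report the action taken at each 2/6 cohort, how 8.3.2 was applied, and the all-patient DLT incidence at the chosen level.

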age of 57 years with the following cytogenetic profiles by MRC criteria [12]: cytogenetically favorable (n=4), intermediate (n=43), adverse (n=13), and unknown (n=1). The study investigated mitoxantrone at 12 mg/m², 14 mg/m², 16 mg/m², and 18 mg/m² (rather than 10 mg/m² as used in the original G-CLAM regimen), and the highest dose level was found to have acceptable toxicity and tolerability. Among the 57 treated patients that are thus far evaluable for response, the overall response rate (ORR) was 87.7% with 75.4% achieving a CR, 5.3% a CR with incomplete platelet recovery (CRp), and 7.0% a CR with incomplete blood count recovery (CRi). Of the responders (including CRp/i), 90.0% had no evidence of MRD by flow cytometry at best response (MRDneg). Overall, the MRDneg CR rate for all patients was 68.4%. Generally, the regimen has been well tolerated, with neutropenic fever, rash, nausea, and hypoxia (fluid overload/infection-related) seen as the most common grade ≥ 3 adverse events. Our phase 2 study is now ongoing with mitoxantrone at the 18 mg/m² dose level, and G-CLAM continues to serve as our principal treatment for newly-diagnosed AML. The MRDneg CR rate from this study will serve as the null rate for comparison with G-CLAM plus sorafenib.

Sorafenib

Sorafenib is an oral, small molecular, multikinase inhibitor which affects specific targets that are critical for tumor cell proliferation including the serine/threonine kinases c-Raf and B-Raf and the receptor tyrosine kinases RET, Flt-3 and c-Kit [13]. Sorafenib has potent *in vitro* activity against receptor tyrosine kinases important in tumor angiogenesis including the vascular endothelial growth factor receptor family (VEGFR1-3) and platelet derived growth factor-beta (PDGFR) [13]. In vivo, the anti-tumor activity of sorafenib is driven by its direct effects on tumor growth through its inhibition of the Raf/MEK/ERK pathway and the anti-angiogenic activity of the compound. Sorafenib demonstrates broad anti-tumor activity in human tumor xenograft models of liver, kidney, lung, prostate, breast and leukemia.

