2.0 OBJECTIVES

2.1 Primary Objective

- 2.1.1 For phase 1, to assess the maximum tolerated dose (MTD) of sorafenib used in combination with dose-intensified mitoxantrone as part of the G-CLAM regimen in adults with newly-diagnosed AML/high-risk myelodysplastic syndromes (MDS).
- 2.1.2 For phase 2, to determine if the addition of sorafenib to G-CLAM improves the rate of MRDneg CR compared with our center's historical control of G-CLAM alone in adults with newly-diagnosed AML/high-risk MDS.

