Level -1	Mitoxantrone10 mg/m ²	Sorafenib 200 mg once daily

In addition to safety stopping rules in phase 1, we will also employ efficacy stopping rules to make sure that the regimen does not have lower response rates than our current standard. Among the first 57/61 evaluable patients treated with G-CLAM alone in our ongoing phase 1/2 study, the MRDneg CR rate was 68%. We will assume that the G-CLAM+sorafenib regimen will not be of further interest if the true MRDneg CR rate is 60% or less (null hypothesis) and that that an MRDneg CR rate of 80% or more would be of interest for further investigation (alternative hypothesis). Therefore, if MRDneg CR is seen in < 5 of the first 11 patients, consideration will be given to stopping the study. An 80% confidence interval for an MRDneg CR rate of 4/11 is 0.17-0.60. Thus the upper bound of this limit is less than the current MRDneg CR rate with G-CLAM alone (68%). However, because the first 11 G-CLAM + sorafenib patients may differ with respect to cytogenetics/age etc. from the original 57 G-CLAM patients, a decision to stop would also depend on comparative examination of patient characteristics.

14.2 Phase 2

The study will be conducted in two sequential parts. The phase 1 portion ends once an MTD is identified or dose level 6 has been completed, whichever occurs first. Patients enrolled in the Phase 1 portion and treated at the MTD dose of sorafenib and mitoxantrone will be included in the analysis of the Phase 2 portion. The primary objective of the Phase 2 portion is to evaluate the MRDneg CR rate after up to 2 courses of induction chemotherapy.

A two-stage design will be used (Simon Optimal Two-Stage). As per the phase 1 section above, the MRDneg CR rate of our historical control of G-CLAM alone is 68%. G-CLAM+sorafenib will not be of further interest if the true MRDneg CR rate is 60% or less (null hypothesis) and that that an MRDneg CR rate of 80% or more would be of considerable interest for further investigation (alternative hypothesis). Therefore, in the first stage, 19 eligible patients will be accrued. If necessary, the study may be temporarily closed while remission data is collected. If at least 12 of the first 19 patients achieved an MRDneg CR (63%), we will move to the second stage. The second stage would enroll another 22 patients (for a total of 41), with G-CLAM + sorafenib considered of interest (at least 80% MRDneg CR rate) if at least 31/41 attained

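### Phase 2 tests a 60% null although Section 1.0 names the G-CLAM rate (68.4%) as the null, so just meeting 31/41 is not by itself evidence of improvement over G-CLAM

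*Combined protocol and SAP*

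**What the plan says.** Section 1.0 (Background, G-CLAM) reports the centre's earlier study of G-CLAM alone, with 57 patients evaluable for response: "Overall, the MRDneg CR rate for all patients was 68.4" per cent. It then commits to a use for that figure: "The MRDneg CR rate from this study will serve as the null rate for comparison with G-CLAM plus sorafenib".

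Objective 2.1.2, the primary objective for phase 2, is "to determine if the addition of sorafenib to G-CLAM improves the rate of MRDneg CR compared with our center's historical control of G-CLAM alone".

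Section 14.2 describes the design: "A two-stage design will be used (Simon Optimal Two-Stage"). It restates that "the MRDneg CR rate of our historical control of G-CLAM alone is 68" per cent, and the next sentence says "G-CLAM+sorafenib will not be of further interest if the true MRDneg CR rate is 60% or less (null hypothesis"). On the other side, "an MRDneg CR rate of 80% or more would be of considerable interest for further investigation (alternative hypothesis"). The trial continues past stage 1 with at least 12 of 19 responders. After 22 more patients it ends "with G-CLAM + sorafenib considered of interest (at least 80% MRDneg CR rate) if at least 31/41 attained" MRD-negative CR. The stated properties are a type I error of 10%, power of 80%, a 51% chance of stopping early under the null, and an average of 29 patients. No other formal phase 2 comparison with the 68% control is described.

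**The concern.** Three current parts of the protocol describe the same test differently. The background names the G-CLAM rate as the null, and the objective asks for improvement over G-CLAM. The decision rule tests a value 8 points below the G-CLAM rate that Section 14.2 has just quoted. Nothing in Section 14 explains the step from 68% to 60%.

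This matters because the rule is the only formal phase 2 test that serves the objective. If 31/41 is reached, the conclusion the design supports is that the rate exceeds 60%. The objective invites a different sentence, that sorafenib improved the rate. The parenthesis in Section 14.2 that equates 31/41 with a rate of at least 80% invites a stronger one still.

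Section 14.1 does treat 68% as the benchmark. Its phase 1 futility rule is justified by an upper confidence bound that falls below 68%.

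**Working it through.** **Inputs.** Stage 1: at least 12/19. Final: at least 31/41, with 22 patients in stage 2. Null 60%, alternative 80% (all Section 14.2). Control 68.4% of 57 (Section 1.0). The count of 39 is inferred from 0.684 × 57 = 38.99. Section 14.2 rounds the control to 68%.

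**Formula.** For a true rate p and final cut-off r,

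P(go | p) = Σ over x = 12 to 19 of P(X = x) × P(Y ≥ r − x), with X ~ Bin(19, p) and Y ~ Bin(22, p).

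Early stopping is P(X ≤ 11), and the average size is 19 + 22 × P(X ≥ 12).

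**1. The plan's own figures, p = 60% and 80%, r = 31.**

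| Property | Stated | Recomputed |
|---|---|---|
| Type I error at 60% | 10% | 2.7% |
| Power at 80% | 80% | 81.5% |
| Early stopping at 60% | 51% | 51.2% |
| Average size at 60% | 29 | 29.7 |

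All but the type I error reproduce. With r = 31, the 10% error is found at p = 65% (10.05%).

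**2. The same rule when sorafenib adds nothing.** At p = 68% the terms for x = 12 to 19 are:

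| x | P(X = x) | P(Y ≥ 31 − x) | Product |
|---|---|---|---|
| 12 | 0.1692 | 0.0461 | 0.0078 |
| 13 | 0.1936 | 0.1202 | 0.0233 |
| 14 | 0.1764 | 0.2458 | 0.0434 |
| 15 | 0.1249 | 0.4132 | 0.0516 |
| 16 | 0.0664 | 0.5933 | 0.0394 |
| 17 | 0.0249 | 0.7522 | 0.0187 |
| 18 | 0.0059 | 0.8686 | 0.0051 |
| 19 | 0.0007 | 0.9397 | 0.0007 |

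The sum is 0.190. At p = 39/57 it is 0.206. In the 39/57 case 77% of trials pass stage 1.

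**3. What the minimum pass shows.** 31/41 = 75.6%. The one-sided 90% Clopper-Pearson lower bound is 64.9%, treating the 41 as a fixed sample. It excludes 60% but not 68%. The corresponding 80% interval is 64.9% to 84.3%, so 31/41 does not establish a rate of at least 80% either.

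**4. What would exclude the control at N = 41, keeping the 12/19 gate.**

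| Final cut-off | P(go) at 68.4% | P(go) at 80% | One-sided 90% lower bound |
|---|---|---|---|
| 31/41 | 20.6% | 81.5% | 64.9% |
| 32/41 | 12.1% | 70.3% | 67.6% |
| 33/41 | 6.3% | 56.2% | 70.2% |

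The lowest cut-off with error at or below 10% against a fixed 68.4% is 33/41.

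**5. Uncertainty in the control.** The exact 80% interval for 39/57 is 59.2% to 76.6%. Steps 2 and 4 take the control as known.

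**The case against.** The best defence is that Section 14.2 describes a screening rule. Its language concerns whether the regimen deserves further study, and it words the phase 2 objective as evaluating the rate after up to two courses. No passage says that 31/41 establishes superiority to G-CLAM. That is correct, and a screening null below the control is a legitimate choice. It does not remove the conflict with Section 1.0, which names a different null, or with 2.1.2, which asks about improvement.

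The 60% also looks deliberate. Section 14 gives it twice, each time near the 68%. It lies close to the lower 80% limit of 39/57 (59.2%). Section 1.0 also puts MRD-negative CR at about three quarters of a 75–80% CR rate, which is 56–60%. Either could be a reason, but the protocol offers neither as one.

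The practical gap is smaller than 8 points. Because the actual error at 60% is 2.7%, the rule works like a 10% test of about 65%, some 3 points under the control. This stands, and it limits the size of the problem.

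A reader might infer that meeting the rule can never show improvement. That goes too far: 31/41 is only the minimum pass, and 33/41 or more would exclude 68%. At a true rate of 80%, 0.562/0.815 = 69% of passing trials would reach 33/41. A reader might also infer that the sponsor intends to report 31/41 as superiority. The documents do not say so.

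**Conclusion.** The inconsistency is real and sits in the current text of the primary phase 2 objective and its decision rule. Just meeting 31/41 supports a rate above 60%. It is not by itself evidence of improvement over G-CLAM. A regimen equal to G-CLAM passes 19.0% (true rate 68%) to 20.6% (68.4%) of the time, against the 10% that the plan states for declaring an uninteresting therapy of interest. The plan defines that 10% at 60%, where the rule's actual error is 2.7%.

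These figures assume independent patients with one common response rate, adherence to both stage rules, and a control rate known without error. The last assumption is generous to any claim of improvement. The label equating 31/41 with at least 80% is unsupported as a reading of the result. It may have been meant as shorthand for the alternative hypothesis.

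**What to change.** Make Sections 1.0, 2.1.2 and 14.2 describe one test, with no added patients:

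- In 14.2, keep 31/41 as the rule for further interest against a 60% null, and give the reason for 60%.
- In 1.0, remove or correct the sentence that names the G-CLAM rate as the null.
- Reword 2.1.2 so that meeting 31/41 is not reported as improvement over G-CLAM. Commit to reporting the observed rate with its confidence interval beside the control (39/57, 68.4%, exact 80% interval about 59% to 77%).
- In 14.2, state the 19–21% pass probability at the control rate, and replace the 10% error with 2.7% at 60%.
- Delete the parenthesis that gives 31/41 the meaning of a rate of at least 80%.

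A formal improvement claim at N = 41 is optional. The lowest cut-off would be 33/41, with 6.3% error against a fixed 68.4% and about 56% power at 80%. It ignores the uncertainty in the control: 33/41 against 39/57 gives a one-sided Fisher P of 0.13. It should carry that caveat if used.

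The cost is wording, plus less favourable stated properties for any comparison with G-CLAM.

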MRDneg CR. The probability of declaring a therapy of interest when it is not is 10% (type-1 error), and not of interest when it is, is 20% (power 80%). Under the null hypothesis (true MRDneg CR rate 60%) the probability of termination before enrolling 41 patients is 51% and the average sample size is 29 patients. Note that patients treated at the recommended sorafenib and mitoxantrone doses during the Phase 1 part of the study would count toward the first 19 patients. Patients will be considered not evaluable if they received less than 75% of the assigned doses of each chemotherapeutic agent during Cycle 1, and they will be replaced. If a patient does not receive at least 75% of their assigned dose of sorafenib but discontinues the drug due to toxicity, they will be considered evaluable as we want to capture this essential toxicity data (and its potential downstream effect on efficacy) and not be replaced.

QOL scores, resource utilization, and cost variables will be recorded and summarized using descriptive methods including boxplots, histograms, and statistical summary measures (medians, means, standard deviation, N, and proportions). This study will not be powered to detect statistically significant differences between these endpoints for those with different responses; rather we will record these outcomes to inform a subsequent larger study, should follow up investigations be warranted.

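### Phase 2 reads its MRDneg CR rule only at 19 and 41 patients, so enrolment can continue after the threshold is out of reach; a one-sentence futility closure would avoid this at no cost in error rates

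*Combined protocol and SAP*

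**What the plan says.** Section 14.2 of the combined protocol and SAP describes a single-arm Simon two-stage design with a null MRDneg CR rate of 60% and an alternative of 80%. The historical rate on G-CLAM alone is given as 68%. For accrual, "in the first stage, 19 eligible patients will be accrued". The first reading is: "If at least 12 of the first 19 patients achieved an MRDneg CR (63%), we will move to the second stage". Then: "The second stage would enroll another 22 patients (for a total of 41), with G-CLAM + sorafenib considered of interest" if at least 31 of the 41 reach MRDneg CR. The endpoint is judged after up to two induction courses.

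The section states a type I error of 10%, power of 80%, a 51% chance of termination before 41 patients under the null, and an average sample size of 29. It also says that "patients treated at the recommended sorafenib and mitoxantrone doses during the Phase 1 part of the study would count toward the first 19 patients".

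Four other provisions come near this point:
- an optional temporary closure while remission data are gathered (14.2);
- a phase 1 look that considers stopping if fewer than 5 of the first 11 patients reach MRDneg CR (14.1.2);
- committee review at least once a year (12.0);
- a general right of the investigator, IRB or FDA to terminate (15.0).

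None closes phase 2 enrolment on a count of failures.

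**The concern.** Both thresholds can become unreachable well before they are read. After that, a new patient still receives intensive chemotherapy plus sorafenib, but the outcome cannot change the decision that the plan has set for itself.

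The carry-over of phase 1 patients sharpens this. Their outcomes can be known before phase 2 opens, and a phase 1 cohort may hold up to 12 patients (14.1.2). If 8 of 12 carried-over patients had already failed, the text would still have 19 − 12 = 7 more enter before the stage 1 rule is read.

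**Working it through.** **Inputs (14.2).** n1 = 19, continue if at least 12; n = 41, success if at least 31; null 60%, alternative 80%. I add 68%, the historical rate.

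**Deciding failures.** Stage 1: 19 − 8 = 11, which is below 12, so the 8th failure decides. Overall: 41 − 11 = 30, which is below 31, so the 11th failure decides.

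**The plan's own figures first.** With X1 the number of responders among the first 19:
- Probability of early termination, PET = P(X1 ≤ 11 | 19, 0.60) = 0.512 (stated 51%).
- Average N = 19 + 22 × (1 − 0.512) = 29.7 (stated 29).
- P(declare interest) = Σ over x = 12 to 19 of P(X1 = x) × P(X2 ≥ 31 − x | 22, p). This gives 0.815 at 80% (stated power 80%) and 0.027 at 60% (stated type I error 10%).

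The first two figures reproduce without any early closure. With closure at the deciding failure the average would be 23.5, so no such closure is built into the stated 29. The 2.7% against 10% is a separate inconsistency. It matters here only because the count of 11 depends on the 31/41 cutoff.

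**Adding the stop.** I enumerated patient by patient, stopping at the 8th failure within the first 19 or the 11th overall. The stop acts only on sequences that can no longer succeed, so P(declare interest) is identical: 0.0271 at 60% and 0.8149 at 80%.

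Saving with immediate readout = P(stage 1 fails) × (19 − mean deciding patient) + P(stage 2 fails) × (41 − mean deciding patient):
- 60%: 0.5122 × (19 − 15.79) + 0.4607 × (41 − 31.14) = 1.64 + 4.54 = 6.2
- 68%: 0.2381 × (19 − 16.47) + 0.5721 × (41 − 33.56) = 0.60 + 4.26 = 4.9
- 80%: 0.0233 × (19 − 17.15) + 0.1618 × (41 − 36.38) = 0.04 + 0.75 = 0.8

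**Response lag.** Each marrow is read at count recovery or Day +28 to +35 (6.6, 6.7), and failure is final only after up to two courses. The documents give no accrual rate, so the number L of patients who enter between the deciding failure and its readout is an assumption. If k is the deciding patient, the saving is the mean of max(0, 19 − k − L) in stage 1, or max(0, 41 − k − L) in stage 2.

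| True rate | Average N, as planned | Average N, stop with L = 0 | Saved, L = 0 | Saved, L = 3 | Saved, L = 6 | P(failure settled before the planned reading) |
|---|---|---|---|---|---|---|
| 60% | 29.7 | 23.5 | 6.2 | 3.8 | 2.1 | 0.89 |
| 68% | 35.8 | 30.9 | 4.9 | 2.9 | 1.5 | 0.73 |
| 80% | 40.5 | 39.7 | 0.8 | 0.39 | 0.17 | 0.16 |

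The last column is for L = 0.

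**Carried-over phase 1 patients.** P(at least 8 failures among 12) is 5.7% at 60%, 1.4% at 68% and 0.06% at 80%. With 8 carried over it is 0.4^8 = 0.07% at 60%. With 6, the basic cohort size, it is zero.

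**Dependence on the final cutoff.** A final cutoff of 29/41, shown only as an example, gives a type I error of 9.9%. The deciding failure overall would then be the 13th (41 − 13 = 28). The saving at 60% would be 4.1, 2.0 and 0.8 patients for L = 0, 3 and 6. The stage 1 count stays at 8.

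**The case against.** The strongest reply is that nothing is broken. Reading a Simon design only at the end of each stage is the usual and valid form, and the stated 51% and 29 describe that form. This stands: the point is an improvement, not an error.

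A reader might infer that patients will always be enrolled needlessly, or that about six are wasted. The documents do not support either. Needless enrolment depends on the true rate and is uncommon at 80%. The figure of 6.2 needs instant outcomes, which a two-course endpoint rules out.

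The carry-over example is also an extreme. It needs at least 8 counted phase 1 patients, and even with 12 it is unlikely at 60% or 68%.

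The trial is open-label at a single centre, the investigator reviews data often, and enrolment may be paused or ended at discretion. That makes it less likely that a lost stage would go unnoticed. It does not supply a rule: the pause is optional, the 5-of-11 look belongs to phase 1 and may read patients at other dose levels, and committee review may be only annual.

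Finally, an early stop has costs for estimation, and a hard-coded 11 could wrongly close a trial whose final cutoff had been lowered. Both objections stand and shape the proposed change.

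**Conclusion.** The point holds as a cheap improvement. Section 14.2 allows enrolment after its own threshold has become unreachable, and none of the discretionary provisions reliably closes that gap. Under the current cutoffs, and if 3 to 6 patients enter before an outcome is known, a closure rule would spare about 2 to 4 patients at a true rate of 60%, 1.5 to 2.9 at 68%, and fewer than 0.4 at 80%. Type I error and power do not change. The lag is assumed, and the savings in stage 2 depend on 31/41 standing. It would be wrong to read this as a fault in the operating characteristics: the gap between 2.7% and the stated 10% comes from the final cutoff and would remain with or without an early closure.

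**What to change.** Add to 14.2 that enrolment closes for futility once the number of evaluable patients known not to have MRDneg CR after up to two courses means that the current stage's threshold can no longer be reached. Give the counts as a consequence of the rule: 8 in stage 1, and 11 overall if 31/41 stands, to be recalculated if that cutoff is reconciled with the stated 10% type I error. Count known failures among carried-over phase 1 patients before phase 2 opens. Add no early stop for success. Restate the average sample size, with the lag assumed.

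The cost is a sentence or two of text and a running tally of failures. There are two downsides. A trial that has already failed will have fewer patients for the secondary and toxicity estimates. The raw MRDneg CR proportion after an early stop is biased downward, so it should be reported with an estimate adjusted for the stopping rule.
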